Pilot testing of each component of the ACT intervention began in April 2020 (IRB 20-004204). During the first phase of testing, the electronic health record indicator was optimized to identify candidate individuals for the ACT intervention. Alerts were manually validated and cross-referenced with clinical notes and nephrology service rosters. During the second phase of testing, the feasibility of the nurse education visit was evaluated. A nephrology nurse liaison successfully visited all 18 patients targeted for education. The nephrology consultation service, and by extension the nurse liaison, was not previously following 7 (39%) of these individuals. In the third testing phase, 11 individuals consented to participate and were placed on the AKI survivor care path. Of these individuals, one died before discharge, one was discharged on dialysis, and one did not receive education from the nurse liaisons before discharge. In the remaining eight patients, 100% completed an encounter with the PCP, a serum creatinine evaluation, and urinalysis within two weeks of discharge [median time to follow up 2 (IQR 1, 6) days]. Six (75%) completed an encounter with a pharmacist 5 (1, 10) days after discharge. Two (25%) patients consulted with an outpatient nephrologist on day one and day 22 after discharge, respectively. Over time, kidney health knowledge improved in the majority of patients. In the majority of patients who received education [from a nurse (phase 2) or a nurse + primary care provider +/- pharmacist (phase 3)], knowledge scores improved immediately after education delivery and remained improved for 2-4 weeks thereafter.

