**Patients:** Participants will be recruited from those identified by a developed electronic health record list of patients with AKI. Included individuals that populate the list are those with stage III AKI (severe) during a hospitalization based on serum creatinine rise or urine output decline from Olmsted County. The EHR list which includes these criteria was developed, tested, and refined for accuracy and completeness as part of IRB 20-004204 (see above preliminary data). Screened individuals with dementia, those who are non-English speaking, or expected to dismiss to a skilled nursing facility at discharge will be excluded. Individuals who are expected to need dialysis at discharge or who are discharging on hospice will be excluded. If the patient is actively enrolled in the Primary Care Transitions Program at hospitalization they will be excluded. Recipients of any transplant, including solid organ, hematopoietic stem cell, or CAR-T, within 100-days of enrollment will also be excluded. Individuals may only be enrolled in the trial one time. Trained study team members will approach potential candidates during their hospitalization to obtain written informed consent. Individuals will be provided with information about the research, HIPAA Authorization, and IRB approved consent forms for review. Sufficient time will be allowed for discussion and patient questions. Patients will be informed that declining to participate in the study will not impact the care that they receive. Consent will be obtained in person where possible, but may be obtained via telephone call depending on the safest mode of contact due to

COVID-19. All consenting patients will be included in the clinical trial. No reimbursement or remuneration will be provided for participation.

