Study team members will review video/audio recordings to assess the impact of the ACT intervention on the encounter. Reviewer(s) will watch the video (if available) and read the transcripts for the clinical encounter. Based on the literature, encounters will be primarily evaluated for six elements of kidney health follow-up for AKI survivors: Kidney function, advocacy/education, medication reconciliation/review, blood pressure, sick day counseling, and a follow-up plan. Twenty percent of the recorded encounters will be reviewed by two study team members independently and in duplicate. Concordance between individuals in assigned ratings of the six elements will be evaluated. If greater than 0.8, reviewers will be considered concordant and one study team member will evaluate the remaining encounters. If concordance is not met, an additional 20% of the included encounters will be evaluated in duplicate. The duration of time (minutes) spent on each element will be catalogued. Reviewers will record whether the clinician utilized the ACT 'best practice advisory' in the electronic health record, or any AKI or kidney health handouts or print or electronic materials during the clinical encounter. In primary care encounters, occasions where kidney health was discussed will be catalogued as clinician-initiated or patient-initiated.

**Patient-reported outcomes:** We will evaluate patient knowledge about AKI measured with an adaptation of the Kidney Knowledge Survey (modified KiKS; mKiKS). mKiKS assesses participants' objective knowledge about AKI causes, risk factors, and management. Unanswered questions (missing data) on the mKiKS are assigned a score of 0, and the total score is used for comparisons. mKiKS will be evaluated at randomization and 30 +/- 7 days post-discharge in all patients. Quality of life will be assessed at randomization and 30 +/- 7 days post-discharge in all patients using the PROMIS Global 10 tool (v1.2). The aforementioned "Was it worth it?" survey will be performed at 30 +/- 7 days post-discharge. Patient-reported outcomes will be collected in person or over the phone by a study team member (estimated time to complete in pilot testing is 15 minutes).

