### Statistical analysis

**Analysis plan:** To describe the feasibility of ACT and generate preliminary estimates of the effect on patient reported and clinical outcomes, descriptive analyses will be conducted in three groups 1) the intention to treat population (anyone randomized), 2) the per protocol population (randomized patients who receive the assigned study intervention; in the case of ACT patients this would include completion of nurse education, laboratory testing, pharmacist visit, and primary care provider visit), and 3) the complete follow-up population (the per protocol population with follow-up patient reported outcomes at 30 +/- 7 days). Baseline characteristics will be described with means and standard deviations and counts and percentages and compared using t-tests and chi-squared tests, respectively. Any baseline imbalances ( $p < 0.05$ ) will be explored as a possible factor to adjust for when the outcome measures are analyzed. The CONSORT guidelines will be followed to transparently report study results.

AKI knowledge will be described between groups with the mean mKiKS score. In patients with incomplete follow-up, model imputation will be used to impute follow-up scores. Mean between-group differences in the total baseline and follow-up scores will be compared using the t-test or non-parametric Mann Whitney U test. An exploratory multivariable linear regression model will be fit with group assignment as the independent predictor of interest, mean follow-up knowledge scores as the dependent variable, and baseline scores as a covariate. Other variables to be considered will include age, sex, baseline health literacy, socioeconomic status, and baseline comorbidities, specifically CKD. Clinical outcomes up to 12-months will be compared with Cox proportional hazards models.

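### Missing 30-day mKiKS scores are imputed by an unnamed model, then tested with no stated step that carries imputation uncertainty into the result

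*Combined protocol and SAP*

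**What the plan says.** The Statistical analysis section gives wholly missing 30-day surveys one sentence: "In patients with incomplete follow-up, model imputation will be used to impute follow-up scores". The next sentence says that between-group differences in baseline and follow-up totals "will be compared using the t-test or non-parametric Mann Whitney U test". It then adds: "An exploratory multivariable linear regression model will be fit with group assignment as the independent predictor of interest". That model has the follow-up score as outcome and the baseline score as covariate.

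Other parts of the document bear on this:

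- **Outcomes, patient-reported outcomes:** "Unanswered questions (missing data) on the mKiKS are assigned a score of 0, and the total score is used for comparisons". This rule covers single items, so imputation matters only for surveys that are absent altogether.
- **Analysis sets:** intention to treat is everyone randomised. The only set that requires an observed 30-day score is the complete follow-up set, which is a subset of the per-protocol set.
- **Aim 2:** the knowledge result is to be assessed in the intention-to-treat population.
- **Randomization:** allocation is stratified by hospital service.
- **Sample Size:** 25 per group, a 2-point (12.5%) difference, SD 15%, two-sided alpha 0.05 and 80% power. No missing-survey rate is stated separately.

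**The concern.** The plan commits to imputing but leaves open the details on which the answer depends. It does not name the predictors, the number of imputed data sets or a pooling rule, and it does not say whether group enters the model.

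Two ways of carrying out the sentence as one filled-in data set go wrong differently. If group is in the model, the test treats imputed values as observed and the interval is too narrow. If group is left out, imputed patients in both arms are pulled towards a common value and the difference shrinks.

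No planned analysis would reveal either effect, because the complete follow-up set also conditions on receiving the full assigned intervention. At stake is the preliminary estimate of effect on knowledge, and its precision, which a later trial would draw on.

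**Working it through.** **1. The plan's own figure.** With difference 12.5 and SD 15 (Sample Size), n per arm = 2 × (1.960 + 0.842)² × (15/12.5)² = 2 × 7.85 × 1.44 = 22.6, so 23. The t-test version needs 24, and power at 25 is 0.82. The stated 25 is sound. Two points as 12.5% implies a 16-point scale (2/0.125).

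**2. Benchmark with 50 complete surveys.** SE = 15 × √(2/25) = 4.24. The 95% interval width is 2 × 2.011 × 4.24 = 17.1 (17.0 in simulation).

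**3. Group left out.** Imputed scores do not depend on arm, and baseline is balanced on average. The expected difference is therefore about (1 − m) × 12.5, where m is the proportion missing:

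- m = 4%: 12.0
- m = 10%: 11.25
- m = 20%: 10.0
- m = 28%: 9.0

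**4. Group in the model, predicted values filled in.** At 20% missing and baseline correlation 0.5, simulation gives a mean reported SE of 3.88, while the estimate's actual SD is 4.57. The ratio is 3.88/4.57 = 0.849. The nominal cut-off of 2.011 then acts like 2.011 × 0.849 = 1.71, which gives coverage of about 91% and type I error of about 9% (simulated: 0.092). The reported SE is below even the 4.24 for complete data, so losing surveys would appear to add precision.

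**5. Range of settings.** The runs used 20,000 simulated trials per setting (Monte Carlo error about ±0.003), 25 per arm, SD 15, and a true difference of 0 or 12.5. Three inputs are assumptions because the documents do not give them: the missing rate, the baseline correlation (0.3, 0.5, 0.7) and the mechanism (completely at random, or more likely with a low baseline score). All rows are one imputation followed by a t-test. The group-in-model columns cover both predicted values and predictions with a random residual.

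| Assumed missing | Group in model: coverage | Group in model: type I error | Group left out: mean difference (true 12.5) | Group left out: coverage |
|---|---|---|---|---|
| 4% | 94-95% | 5-6% | 11.9-12.0 | 95% |
| 10% | 92-94% | 6-8% | 11.2 | 93-94% |
| 20% | 88-92% | 8-12% | 9.9-10.0 | 90-91% |
| 28% | 85-91% | 9-15% | 8.9-9.0 | 83-87% |

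With group left out, type I error stays at 0.047-0.053, so the harm there is to the estimate. A Mann-Whitney test on predicted values is no safer: its type I error is 0.073-0.145 at 20% missing.

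**6. Methods with valid variance, same settings** (multiple imputation on 4,000 trials, error about ±0.007).

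- Multiple imputation with 50 data sets and Rubin's rules: the t-test covers 95-96% at every rate, and the adjusted model has type I error 0.042-0.052. Health literacy was also in this imputation model. A further simulation with only group and baseline score, and 20 data sets, held type I error at 0.036-0.050 for 12-40% missing.
- Adjusted model on observed scores, no imputation: type I error 0.045-0.054. Its interval width at 20% missing is 14.1-18.8, against 14.4-19.3 for the adjusted multiply imputed model.

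**The case against.** The strongest reply is that the plan never says single imputation, nor that the tests run on one filled-in data set. A reader might infer that the planned analysis is invalid. The text does not support that; it supports only under-specified, and the distortion follows from one reading.

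Second, nothing shows that many surveys will be missing. Collection is short and can be done by telephone, and the 70% in Sample Size already includes having usable outcome data. A reader might take the pilot losses as a missing-survey rate: "Of these individuals, one died before discharge, one was discharged on dialysis, and one did not receive education from the nurse liaisons before discharge". They are not one. Patients expected to need dialysis at discharge are now excluded, missing the nurse's education is not missing a survey, and no survey-completion rate is reported.

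Third, the analyses are described as descriptive, enrolment rests on expected recruitment, and no confidence interval is mentioned. That lowers the weight of the point. It does not remove it, because the plan names tests and quotes power for this outcome.

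Fourth, a reader might conclude that multiple imputation is required. It is not: under the mechanisms simulated, the adjusted model on observed scores is also valid.

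A reader might also infer that patients who die would be given a knowledge score. The plan is silent on this, and it is a separate question about what is being estimated.

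All four replies stand as limits. None supplies the missing specification.

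**Conclusion.** The concern holds as a gap in specification with a conditional harm, and it should be fixed. The omission is certain: no part of the document gives the imputation type, predictors or pooling. The harm arises only if the sentence is carried out as one filled-in data set. It is then small at about 4% missing, modest at 10% and material from about 20%, where coverage is 88-92% with group in the model, or about a fifth of the true difference is lost with group left out. These sizes rest on assumed missing rates, correlations of 0.3-0.7 and missingness unrelated to the unseen score. They say nothing about surveys missing because knowledge or health is worse.

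**What to change.** Replace the imputation and testing sentences with text to this effect:

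> The main intention-to-treat mKiKS estimate is the group coefficient, with 95% confidence interval, from a linear model of the 30-day score on group, baseline mKiKS and randomisation stratum. Wholly missing surveys are handled by [one, chosen in advance]: (a) multiple imputation with group, baseline mKiKS and stratum in the imputation model, pooled by Rubin's rules; or (b) fitting the same model to all randomised patients with an observed score.

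In addition:

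- Do not run a t-test or Mann-Whitney test on a singly imputed data set. If Mann-Whitney is kept, run it on observed scores only, as supportive. This avoids having to pool a rank test.
- Add a sensitivity analysis that departs from missing at random, such as shifting imputed scores downward by arm. Options (a) and (b) share that assumption, so neither tests the other. For scale, at 20% missing a one-point shift (100/16 = 6.25 percentage points) in one arm moves the difference by 0.20 × 6.25 = 1.25.
- Report deaths and missing surveys by arm.

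**Cost.** This needs plan wording and a few lines of standard code. No new data are needed, because baseline mKiKS and stratum are already recorded and the baseline score is already in the exploratory model. That model moves from exploratory to main, a choice made for precision.

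Honest intervals are wider. At 20% missing the unadjusted multiply imputed interval is 18.5-19.8 percentage points, against 15.3-16.1 for predicted-value imputation; at 4% the widening is only 0.4-0.8. Baseline adjustment offsets this to a degree that depends on the baseline correlation. At 20% missing, the adjusted multiply imputed interval against the single-imputation t-test is 14.5 v 16.0 at correlation 0.7, 17.5 v 15.6 at 0.5 and 19.3 v 15.3 at 0.3.

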Randomization: Should the patient consent to participate, the individual will randomly be assigned 1:1 to one of two groups, the ACT group (intervention) or usual care (control). Randomization will occur via sealed envelopes which will contain the randomization information. Based on our preliminary data, randomization will be stratified according to hospital service/source: hospital medicine/family medicine or other services. Individuals will be randomly allocated equally to the intervention or control groups within each stratum using a permuted block design with varying block sizes of between 2 and 4. The target sample size is 50 (25 per group). The study coordinator will disclose the group allocation to patients after completing standard informed consent for participation in clinical research including permission to use protected health information.

Intervention: The ACT intervention was approved by the Mayo Midwest Clinical Practice Committee and local discipline specific subcommittees (nephrology, primary care, pharmacy). The intervention workflow was developed and pilot tested as part of IRB 20-004204. A description of the intervention is undergoing peer-review for publication ([name], et al.). As outlined in the preliminary data, patients randomized to the ACT intervention receive a multicomponent transitional support bundle including 1) a consultation from nurse educators before discharge to deliver kidney health education using approved materials available for use by any Mayo Clinic provider or patient (<http://intranet.mayo.edu/charlie/nephrology-hypertension-rst/education/patient/> , <https://askmayoexpert.mayoclinic.org/topic/clinical-answers/cnt-20114555/sec-20114604> ), 2) coordinated appointments for post-discharge laboratory testing (serum creatinine and urinalysis with microscopy), a primary care provider visit, and a pharmacist visit within approximately two weeks of discharge. Each of these elements would be considered standard for an AKI survivor, but the ACT intervention aims to operationalize them more cohesively and consistently to facilitate the care transition. A note will be entered into the patient's EHR to communicate enrollment to the healthcare providers. As an example, a note that may be entered for an intervention patient could be as follows:

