Data will be abstracted from the EHR on patient demographics, comorbidities, attributes of the hospitalization, details about the episode of AKI and the degree of recovery by discharge, follow-up processes of care (laboratory assessments, visits), and clinical outcomes. Core data to be collected will include age, sex, height, weight, race/ethnicity, socioeconomic status, health literacy (using the Brief Health Literacy Screen), history of hypertension, diabetes, cardiovascular disease, chronic kidney disease, or other vascular diseases, hospital and intensive care unit length of stay, reason for admission (non-operative, operative), discharge disposition, whether nephrology was involved with the patient's care during the hospitalization, the severity of AKI, need for dialysis, and discharge kidney function. Select medication data will be collected at baseline (preadmission based on the documented medication list in the EHR), discharge, and 30-day follow-up. This will include the use of angiotensin converting enzyme inhibitors/angiotensin receptor blockers (ACEi/ARBs), sodium glucose co-transporter 2 inhibitors (SGLT2i), metformin, GLP-1 receptor antagonists, sulfonylureas, insulin, loop diuretics, thiazide diuretics, statins, aspirin, non-steroidal antiinflammatory drugs (NSAIDs). The total number of medications at discharge will be evaluated. Using previously described methods, EHR documentation for patients who complete a follow-up encounter with a health care provider (provider, pharmacist, or other), will be reviewed to identify medication discrepancies and drug therapy problems. These will be catalogued for all medications and specifically nephrotoxic or renoprotective medications. Drug therapy problems will be categorized as pertaining to effectiveness, indication, safety, or adherence. Additional data elements may be abstracted from the electronic health record to support the study aims. Data will be collected in a secure REDCap database designed expressly for this study. REDCap (<https://redcap.mayo.edu/redcap/index.php>) is a secure, web-based application that is HIPA compliant and available 24 hours per day. Data will be managed by the trial statistician and the principal investigator.

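### For AKI knowledge, the lead analysis is only implied and left partly open; stating the planned baseline-adjusted regression, with the randomisation stratum added, as the lead estimate would gain precision at no cost

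*Combined protocol and SAP*

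**What the plan says.** The Analysis plan paragraph of Statistical analysis gives two analyses of the mKiKS score. The first is unadjusted: "Mean between-group differences in the total baseline and follow-up scores will be compared using the t-test or non-parametric Mann Whitney U test". The second follows directly: "An exploratory multivariable linear regression model will be fit with group assignment as the independent predictor of interest", with "mean follow-up knowledge scores as the dependent variable, and baseline scores as a covariate". Further covariates are left open: "Other variables to be considered will include age, sex, baseline health literacy, socioeconomic status, and baseline comorbidities, specifically CKD". The same paragraph says that any baseline characteristic differing between groups at p < 0.05 "will be explored as a possible factor to adjust for when the outcome measures are analyzed".

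The Randomization paragraph states: "Based on our preliminary data, randomization will be stratified according to hospital service/source: hospital medicine/family medicine or other services". No analysis in the Statistical analysis section includes that factor.

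Under Outcomes, "mKiKS will be evaluated at randomization and 30 +/- 7 days post-discharge in all patients", so a baseline score is planned for every patient. Aim 2 describes the knowledge outcome as change from baseline to 30 days in the intention-to-treat population. The Sample Size paragraph gives 25 per group to detect 2 points (12.5%) with an SD of 15%, two-tailed alpha 0.05 and 80% power. It does not say whether that SD belongs to a single score or to a change.

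**The concern.** The order of the text and the word exploratory imply that the unadjusted comparison leads. That implied lead leaves two choices open: t-test or Mann-Whitney, and, once Aim 2 is read alongside, follow-up score or change. The analysis that uses the baseline score most efficiently is ranked second, and the factor on which patients are stratified is used nowhere.

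A main product of the pilot is an estimate with an interval for planning the next trial. If the choice among analyses is made after the data are seen, the estimate carried forward may be the most favourable one. If the less precise analysis leads, the interval is wider than the collected data require.

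The baseline screen opens another data-driven route into the model. In a randomised trial, a baseline p-value reflects chance imbalance and does not show whether a variable predicts mKiKS.

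**Working it through.** **Inputs.** From Sample Size: 25 per arm, 2 points = 12.5%, SD 15%, two-sided alpha 0.05. Hence the scale maximum is 2 / 0.125 = 16 and the SD is 0.15 × 16 = 2.4 points. The within-group correlation r between baseline and 30-day scores is not in the documents; it is assumed to be 0.3 / 0.5 / 0.7. The SD is taken as equal at both visits and in both arms.

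**The plan's own figure.** Normal approximation: n = 2 × (1.960 + 0.842)² × (15 / 12.5)² = 22.6, so 23 per arm. The noncentral t gives 24 (power 80.7%), and 25 per arm gives 82.3%. The planned 25 is reproduced as an unadjusted two-sample comparison of means.

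**Formulas at 25 per arm.**
- Follow-up t-test: SE = 2.4 × √(2/25) = 0.679, 48 df. Half-width 2.011 × 0.679 = 1.36.
- Change t-test: multiply the variance by 2(1 − r), 48 df.
- Regression on group, baseline and stratum: multiply the variance by (1 − r²) × 47/46, with 46 df. The factor 47/46 is the expected cost of chance imbalance in baseline score. None is added for the stratum, because permuted blocks nearly balance it; the stratum is taken to explain no variance. At r = 0.5: √(0.75 × 1.0217) × 0.679 = 0.594, and 2.013 × 0.594 = 1.20.

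**Reading 1: 15% is the SD of a single score.**

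| Analysis | Power at r = 0.3 / 0.5 / 0.7 | 95% CI half-width, points |
|---|---|---|
| Follow-up t-test | 82 / 82 / 82% | 1.36 / 1.36 / 1.36 |
| Change t-test | 68 / 82 / 96% | 1.61 / 1.36 / 1.06 |
| Adjusted regression | 85 / 91 / 98% | 1.32 / 1.20 / 0.99 |

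At r = 0 the regression has 81% power and a half-width of 1.38, so the cost is about one point of power. In variance it breaks even with the follow-up t-test when (1 − r²) × 47/46 = 1, that is r = √(1/47) ≈ 0.15.

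**Reading 2: 15% is the SD of change.** The single-score SD becomes 2.4 / √(2(1 − r)) = 2.03 / 2.40 / 3.10 points. Power is then 82% at every r for the change t-test, 93 / 82 / 61% for the follow-up t-test and 94 / 91 / 87% for the regression.

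**Selection among analyses.** Null simulation with normal data, 25 per arm, 20,000 runs per r, counting a rejection whenever the smallest p is below 0.05:
- t-test or Mann-Whitney on follow-up scores: 6.1 / 5.6 / 5.9%.
- Adding the regression on baseline: 7.3 / 7.9 / 9.0%.
- Adding a change t-test as well: 10.2 / 10.1 / 10.9%.

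**The stratum's own contribution.** This depends on an assumed gap in mKiKS between services. With gaps of 0.5 / 0.8 / 1.0 SD, r = 0.5 and equal strata (simulation, 10,000 runs per cell), adding the stratum to the baseline model raises power by about 0.2 / 0.9 / 2.0 points. The type I error of the follow-up t-test that ignores the stratum is 4.2 / 3.5 / 2.5%, so it is conservative.

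**The baseline screen.** The Data collection section says "Core data to be collected will include age, sex, height, weight, race/ethnicity, socioeconomic status, health literacy" and goes on to five groups of prior conditions, which makes 12 pre-admission characteristics. If they were independent, the chance of at least one p < 0.05 would be 1 − 0.95¹² = 46%. If they behaved like five independent variables, it would be 1 − 0.95⁵ = 23%.

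**The case against.** The strongest reply is that the plan already has an order. The unadjusted comparison comes first, the sample size matches it, and the regression is called exploratory. That stands. A reader might infer that the plan has no lead analysis at all, but the documents do not support that: what is missing is an explicit statement, a choice of test, and a choice between score and change. The fix therefore reverses an implied order.

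A reader might also infer that the planned test is invalid or underpowered. It is neither on the plan's own assumptions. The t-test on follow-up scores has 82% power if 15% is the SD of a single score, and leaving out the stratum makes it conservative. The shortfall of a change t-test at r = 0.3 (68%) holds only on that same reading of the SD; if 15% is the SD of change, that test has 82%.

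A reader might quote a type I error of 10 to 11%. That figure counts a change t-test, which the Statistical analysis section does not clearly list. It also supposes that the smallest p would be reported, and nothing in the text says so; the plan calls the analyses descriptive and commits to CONSORT. It is a hypothetical upper bound.

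The gain depends on r, which is unknown. At r = 0.3 it is small: 82% to 85% power, and 1.36 to 1.32 points. This also stands, and the stratum's own gain is smaller still.

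Finally, it is tempting to ask for Mann-Whitney and the baseline screen to be deleted. That goes too far. The score is bounded, with unanswered items scored 0, so a rank test is a reasonable check. The screen only proposes factors to explore, so labelling the resulting models exploratory is enough.

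**Conclusion.** The point holds as a free gain in precision and pre-specification; no invalid analysis is being corrected. The adjusted model has more power than either t-test at each assumed r from 0.3 to 0.7, under both readings of the 15% SD, and stays above 80% throughout (lowest value 85% on the single-score reading, 87% on the change reading). Neither unadjusted t-test does that: the change t-test can fall to 68% and the follow-up t-test to 61%, depending on r and on which SD was meant. The worst case for the adjusted model on the single-score reading is r = 0, where it loses about one point of power.

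Naming the lead also removes a possible inflation of the type I error to about 6% (choice of test) or about 7 to 9% (regression added), if the most favourable result were put forward. These figures assume normal data, equal SDs, 25 evaluable patients per arm and the stated values of r. The sample size needs no change.

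**What to change.** In Statistical analysis, state that the lead estimate for AKI knowledge is a linear regression of each patient's 30-day mKiKS total on group, baseline mKiKS and hospital-service stratum, in the intention-to-treat population, reported as an adjusted mean difference with 95% CI. Remove the exploratory label from this model only.

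Keep the t-test and the Mann-Whitney test, both on follow-up scores, as sensitivity analyses. Keep models with age, sex, health literacy, socioeconomic status, CKD or any factor suggested by the baseline p < 0.05 screen as exploratory only. In Sample Size, say whether 15% is the SD of a single score or of change.

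Aim 2 needs no rewording: with baseline score in the model, the group coefficient is the same whether the outcome is the 30-day score or the change.

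The cost is wording and two degrees of freedom (48 to 46). Baseline score and stratum are already recorded. An analysis of all randomised patients also needs the imputation model to be specified, which is a separate point.
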